PROTOCOL: The Diurnal Rhythm in Natriuretic Peptide Levels

Study Design, Setting, and Location

The prospective, single-center, mechanistic clinical trial was conducted at the Clinical Research Unit (CRU) at the University of Alabama at Birmingham (UAB). The trial was approved by the institutional review board (IRB No: 300004115), and participants provided written and informed consent. Healthy participants were recruited from the Birmingham metropolitan area and the UAB campus.

Study Protocol

After obtaining informed consent, we completed a medical history and physical examination during the screening visit and determined protocol eligibility based on the inclusion and exclusion criteria. Eligible subjects met with a registered dietician, who explained the five days of standardized diet to be consumed before the 24-hour inpatient visit and reviewed instructions for complying with the diet. All the female participants completed the study protocol during the follicular phase of the menstrual cycle.

Each eligible participant was provided five days of a standardized diet and the SpaceLabs 90227 monitor device, which is a 24-hour ambulatory blood pressure monitoring (ABPM) device(31), along with detailed operative instructions. Each day the participants consumed three meals and snacks, which were provided based on the participant preferences and in accordance with macronutrient RDAs, as per the 2005 USDA Guidelines. The standardized study diet was given to each participant comprised of 51% carbohydrate, 31% fats, 18% proteins, ~4.5 gm sodium, and ~2.5 gm potassium. Additionally, the participants were instructed to drink only water and refrain from consuming alcohol or caffeinated beverages. The participants were instructed to consume only the food provided by the CRU metabolic kitchen during the study period.

The five-day diet was followed by an inpatient visit for a 24-hour assessment of NP levels and BP. The patients wore a 24-hour ABPM device starting on day 5, i.e., one day before the inpatient visit. The participants also collected urine for 24-hours before the inpatient visit to assess the adequacy of standardizing the dietary sodium intake. During the inpatient visit, blood was drawn using an intravenous catheter, a total of 5 times during wakefulness (7 am to 10 pm), and 5 times during sleep (10 pm to 7 am). A flexible intravenous catheter was placed in the antecubital space of the arm to avoid repeated need-stick of the patients. The participants were asked to stay supine 30 minutes before each blood draw to rule out any plausible postural influences on the RAAS, BP, and NP system. The light intensity was ensured to be normal day-light during daytime and dim light (<10 lux) for night blood draws. Participants were provided small standardized meals after each blood draw during wakefulness (i.e., 8 am, 11 am, 2 pm, 5 pm, and 8 pm). Subjects were provided distilled water to drink (50-85 ounces), and the amount of water consumed was recorded. The participants also collected urine stratified in the daytime 7 am to 10 pm) and nighttime (10 pm to 7 am) periods during the visit.

24-Hour Ambulatory BP

The 24-hour ABPM was obtained using a standard protocol every 20 minutes between 6 am and 10 pm and every 30 minutes from 10 pm to 6 am using SpaceLabs 90227, starting a day

prior to the 24-hour inpatient visit to allow the participants to become accustomed to the device. The maximum number of analyzable measurements were 48 daytime and 16 nighttime (Total=64).

Statistical Analyses

All statistical analyses were conducted using SAS 9.4 (Cary, NC) and R (R Core Team, Version 4.0.1). The baseline characteristics were compared using descriptive statistics. Continuous variables were summarized as the median and interquartile range (IQR:25th centile, 75th centile). Continuous data were compared using the Wilcoxon rank-sum test. Pearson χ^2 test was used to compare the categorical variables. The range was computed as the difference between the minimum and maximum value of the analyte over the 24-hour period. The range spread (%) was computed as (range/minimum value)*100. The cosinor analysis of the normalized analyte values (normalized to the 24-hour mean value) was conducted using the cosinor2 package in R Statistical Software (R Core Team, Version 4.0.1). This package uses linear regression to identify the cosine curve that best fits the data and tests the overall significance of the cosinor model using an F-ratio.) The 24-hour data was considered rhythmic if it fit the cosinor function i.e., $f(t) = M + AMP * \text{Cos}[(2\pi t)/24 + \phi] + \epsilon_t$, where M refers to the Mesor (rhythm-adjusted mean), AMP refers to the amplitude (difference between peak and M), and ϕ refers to the phase (time of peak). Data was considered rhythmic if the p-value of the R^2 of the cosine function was <0.05. The rhythm parameters are based on the grouped analysis of the lean and obese population groups. The cosinor parameters of interest while comparing the normalized NP rhythms between lean and obese individuals were the amplitude and acrophase. The reported cosinor parameter of interest while comparing the normalized NP and BP rhythms was acrophase. The amplitude and acrophase are defined based on the fitted cosinor curve. Linear regression models were used to assess the relative percentage difference with a 95% confidence interval (adjusted for age, sex, race) for the 24-hour, daytime, and nighttime mean MRproANP, BNP, NTproBNP, renin, and aldosterone levels between lean and obese individuals. This was calculated using the following formula: $(e^\beta - 1) \times 100$ (β coefficient from linear regression). A two-sided type-I error of <0.05 was considered statistically significant for all analyses.

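### Does defining range spread as (maximum − minimum)/minimum overstate the size of the daily rhythm enough to require a change?

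*Combined protocol and SAP*

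**What the plan says.** The Statistical Analyses section gives two definitions. The first is "The range was computed as the difference between the minimum and maximum value of the analyte over the 24-hour period"; the second is "The range spread (%) was computed as (range/minimum value)*100". Neither says whether the calculation is made for each participant or on a group-mean profile, and neither measure is mentioned again.

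The Study Protocol section sets the number of values behind the extremes. Blood was drawn "a total of 5 times during wakefulness (7 am to 10 pm), and 5 times during sleep (10 pm to 7 am"), which makes ten draws. The daytime clock times can be inferred from the meal times, since meals came "after each blood draw during wakefulness (i.e., 8 am, 11 am, 2 pm, 5 pm, and 8 pm"). Night draw times are not listed.

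For rhythm, the same Statistical Analyses section plans a model: "The cosinor analysis of the normalized analyte values (normalized to the 24-hour mean value) was conducted using the cosinor2 package". It adds that "The rhythm parameters are based on the grouped analysis of the lean and obese population groups" and that "The cosinor parameters of interest while comparing the normalized NP rhythms between lean and obese individuals were the amplitude and acrophase". Whether a profile counts as rhythmic is decided by the p-value of the cosinor fit.

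**The concern.** The maximum and minimum of ten noisy values lie further apart, on average, than the true peak and trough. Dividing by the noisy minimum widens the ratio again. A per-participant range spread is therefore above zero even when the analyte does not vary over the day, and it overstates the rhythm when there is one.

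The trial is about the diurnal rhythm of natriuretic peptides, so the size of daily variation is a central description. If a reader took a per-participant range spread as that size, rhythm and error could not be told apart. The unstated unit adds to this, because the same label on a group-mean profile has a different and usually much smaller bias.

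**Working it through.** The documents give no CV, expected amplitude, group size or range-spread result, so there is no figure of the plan's to reproduce. The calculation below is a simulation under stated assumptions.

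**Inputs from the documents:** ten draws, five of them at 8 am, 11 am, 2 pm, 5 pm and 8 pm; range spread = 100 × (max − min)/min; a single 24-hour cosine fitted to values divided by the 24-hour mean.

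**Assumed inputs:** night draws at 10:30 pm, 12:30, 2:30, 4:30 and 6:30 am; independent lognormal error with CV 5% to 20%; rhythm 1 + A·cos with A = 0.15, 0.30 or 0.50; groups of 10 to 40.

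**1. Flat profile, per participant.** With lognormal error, range spread = 100 × [exp(σW) − 1], where σ = √ln(1 + CV²) and W is the range of ten standard normal values, with median 3.024. At CV 10%, σ = 0.0998 and 100 × [exp(0.0998 × 3.024) − 1] = 35%. At CV 5%, 15% and 20% the result is 16%, 57% and 82%.

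**2. With a rhythm, per participant.** On the continuous curve the error-free value is 2A/(1 − A); for A = 0.15 this is 0.30/0.85 = 35.3%. At the ten draw times it averages 34.5%. Simulated medians over 200,000 profiles, peak time uniform:

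| Rhythm | Error-free | CV 5% | CV 10% | CV 15% | CV 20% | Inflation (CV 5–20%) |
|---|---|---|---|---|---|---|
| ±15% | 34.5% | 42% | 57% | 76% | 99% | 1.22–2.87 |
| ±30% | 83.4% | 90% | 104% | 123% | 147% | 1.08–1.76 |
| ±50% | 192.7% | 199% | 216% | 239% | 267% | 1.03–1.38 |

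The ±15% results hardly depend on the assumed night schedule: six schedules gave about 42% and 99% at the two ends.

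**3. Group-mean profile, ±15%, peak at 3 pm, n = 10 to 40.**

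| Peak-time SD | CV 5% | CV 10% | CV 20% |
|---|---|---|---|
| 0 h | 35% to 36% | 36% to 38% | 38% to 45% |
| 2 h | 30% to 31% | 31% to 34% | 33% to 41% |

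With scattered peak times the value can fall below 34.5%, so the direction of the bias is not fixed.

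**4. Cosinor amplitude on the same data.** Twice the amplitude over the mesor, from coefficients averaged across participants, has true value 2 × 0.15 = 0.30. It comes out at 0.30 with a common peak time at every CV and n tried, and at 0.26 to 0.27 with a peak-time SD of 2 hours. That shrinkage follows from exp[−(2π × 2/24)²/2] = exp(−0.137) = 0.87, and 0.30 × 0.87 = 0.26.

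**5. A non-sinusoidal profile.** Adding a ±10% 12-hour component to the ±15% rhythm, without error, raises range spread at the draw times to 41%, while twice the amplitude over the mesor is 0.29. The two measures answer different questions.

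**The case for a change.** The strongest case for a change is that the bias comes from the formula itself and only its size rests on assumptions. At CV 10%, a flat per-participant profile reads 35%, which matches an error-free ±15% rhythm. The remedy would be cheap: the cosinor is already planned, so one could name its amplitude as the size of daily variation, add an interval calculated over participants, and label range spread as an observed excursion.

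The statistical part of this stands. A per-participant range spread should not be read as rhythm size, and the unit should have been stated.

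The step to a change does not stand. Nothing in the plan makes range spread the headline measure, and nothing assigns it to a lean–obese test. The general sentence on comparing continuous data with a rank-sum test follows directly on the baseline characteristics and does not name it. The amplitude proposed as a replacement is, apart from a factor of two, a quantity the plan already names for the peptide comparison. It also has costs: it misses non-sinusoidal swings, which are plausible when meals follow each daytime draw; it shrinks by about 13% at a peak-time SD of 2 hours; and a simple participant bootstrap covers only about 89% to 92% in groups of 10. Range spread needs no model and records what was observed, including real short-term change that the simulated CV treats as error.

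**Conclusion.** No change to the plan follows. The upward bias of a per-participant range spread is real, but its size depends on three things the documents do not give: the unit of calculation, the error CV and the true rhythm. At CV 5% to 20% it ranges from about 1.03 times (±50% rhythm) to 2.87 times (±15% rhythm). On a group-mean profile it is small at CV 5% to 10% and can reverse.

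The cosinor rhythm test and the amplitude and acrophase comparisons do not use range spread, so the plan's conclusions on rhythm are unaffected. Keeping a model-free excursion beside a fitted amplitude is a fair trade-off. The missing unit is a gap that analysts fill when they label the table. The text is in the past tense, so this concerns how a descriptive figure is labelled and read, and no planned analysis has to be altered.

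### The rhythm rule rests on an R²/F-ratio p-value with no stated participant-level unit or df; on pooled rows or a group-mean curve it does not in general hold its 5% level

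*Combined protocol and SAP*

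**What the plan says.** All of the rhythm analysis is in the Statistical Analyses section of the combined protocol and SAP.

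- The data analysed: "The cosinor analysis of the normalized analyte values (normalized to the 24-hour mean value"). Whose mean this is (the participant's or the group's) is not said.
- The test: the package fits a cosine by linear regression and "tests the overall significance of the cosinor model using an F-ratio". The model is written with one error term and no index for participant.
- The decision: "Data was considered rhythmic if the p-value of the R^2 of the cosine function was <0.05".
- The level of analysis: "The rhythm parameters are based on the grouped analysis of the lean and obese population groups".
- The comparison: "The cosinor parameters of interest while comparing the normalized NP rhythms between lean and obese individuals were the amplitude and acrophase". No test, standard error or interval is named for it.

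The Study Protocol section gives the sampling: "a total of 5 times during wakefulness (7 am to 10 pm), and 5 times during sleep (10 pm to 7 am"), so 10 draws per participant. Daytime draw times can be inferred from meals given "after each blood draw during wakefulness (i.e., 8 am, 11 am, 2 pm, 5 pm, and 8 pm"). Night draw times and the number of participants are not stated.

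**The concern.** Three fits are compatible with a grouped cosinor: a regression on all rows pooled, a regression on the 10-point group-mean curve, or separate participant fits combined across people. They give different p-values from the same data, so the rule cannot be reproduced from the text. A single linear regression with one error term and an R² p-value most naturally describes one of the first two, and both treat the errors as independent.

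Repeated sampling does not by itself break that assumption. Three things can move the level:

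1. For pooled rows, scaling to each person's own mean uses up degrees of freedom that the F-ratio still counts.
2. Neighbouring draws in one person may be serially correlated.
3. People may differ in the size or timing of their rhythm.

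At stake is the only stated criterion for rhythmicity, in a protocol whose title is about diurnal rhythm. A weak or absent group rhythm could be called rhythmic more often than the stated 5% implies. On one reading of the normalisation, the pooled test errs the other way and could miss a rhythm.

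**Working it through.** The plan gives no sample size, power or df for this test. The only figure to check is the nominal 5%.

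**Inputs from the documents.** 10 draws per participant; daytime draws taken as 8, 11, 14, 17 and 20 h from the meal times; threshold 0.05.

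**Assumed inputs.** N = 20 per group for the main results (15 and 40 agree within 2 points); night draws every 2 h from 22 h; mean 10 and residual SD 1; exponentially decaying serial correlation; no group rhythm.

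**Step 1. Pooled rows, own-mean scaling, independent errors.** The regression claims 10N − 3 residual df. Own-mean scaling fixes every participant's average at 1. On a common draw grid this removes N − 1 further df, leaving 10N − 3 − (N − 1) = 9N − 2. Treating the division as centring, the true level is

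P( F[2, 9N−2] > Fcrit[2, 10N−3] × (9N−2)/(10N−3) ).

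For N = 20, claimed df are 197 and available df 178. Fcrit = 3.042, and 3.042 × 178/197 = 2.748, so the level is 6.67%. It is 6.65% at N = 15 and 6.71% at N = 40. Simulation with actual division gives 6.8% at N = 20. No correlation or rhythm spread has to be assumed, but a pooled fit and own-mean scaling do.

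**Step 2. Other null settings, own-mean scaling, N = 20.** These are 10,000 simulated trials per row. The mean curve is tested on F(2, 7). The participant-level test is T² = N·b̄ᵀS⁻¹b̄, with F = T²(N−2)/[2(N−1)] on (2, N−2) df, where b̄ and S are the mean and covariance of the participants' (cos, sin) coefficients.

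| Assumed setting | Pooled rows | Mean curve | Hotelling T² |
|---|---|---|---|
| Independent errors | 6.8% | 5.3% | 5.1% |
| Time constant 1 h | 9.3% | 7.3% | 4.5% |
| Time constant 2 h | 17.2% | 14.5% | 4.8% |
| Time constant 4 h | 27.7% | 29.9% | 4.5% |
| Person-to-person cos and sin SD 0.18 residual SD | 9.2% | 6.9% | 5.3% |
| Person-to-person cos and sin SD 0.35 residual SD | 14.9% | 12.3% | 5.0% |

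Independent repeats agree within about 1.5 points. Three other night grids give similar figures (for example 16.8-19.1% pooled and 13.9-15.9% mean curve at 2 h).

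**Step 3. The other reading of the normalisation.** Dividing by the group mean leaves level differences between people in the pooled residual. With no such differences and independent errors, the pooled level is about 4.6-4.8%. With a level SD of one residual SD it is about 0.4-3.5% across independent errors and time constants up to 4 h, which is conservative. The mean-curve results do not depend on this choice.

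**Step 4. Point estimates.** On a complete common grid, pooled, mean-curve and averaged individual fits give the same coefficients (agreement to 3e-16). The choice of fit affects the p-value, not the estimated amplitude or acrophase.

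**The case against.** The strongest reply is that this may be a gap in reporting only. The plan names a dedicated cosinor package and an F-ratio, and a grouped analysis could mean a participant-level population-mean cosinor. Its level would be close to 5%, as the Hotelling results show. This stands: the text does not exclude it. An R² p-value is an odd description of such a test, but the documents do not show what the package prints. A reader might infer that this trial's rhythm calls are inflated, and the documents do not support that.

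Second, the only excess that needs no assumed correlation or rhythm spread is small (6.7% against 5%). It still requires a pooled fit and own-mean scaling, and the plan states neither. Under group-mean scaling the pooled error can run the other way. This also stands, so the claim is that the 5% level is not held in general, not that it is always exceeded.

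Third, a reader might go on to infer that the lean-obese confidence intervals for amplitude and acrophase are too narrow. The plan specifies no interval, standard error or test for those comparisons, so there is nothing to evaluate. The gap there is that no method is named.

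What the reply does not remove is that the rule as described fits the two uncalibrated analyses at least as well as the calibrated one, and that a better-calibrated test is available on the same data.

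**Conclusion.** The point holds in limited form. The omission of unit, df and normalising mean is certain; its effect depends on which fit was used.

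- Pooled rows, own-mean scaling: 6.7% with independent errors, about 9-29% over the assumed range.
- Pooled rows, group-mean scaling with level differences between people: conservative, about 0.4-3.5%.
- Mean curve: 5% with independent errors, about 7-30% over the assumed range, whichever mean is used.
- Participant-level population-mean cosinor: about 5%, and only the reporting needs to change.

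The ranges rest on assumed correlation times, rhythm spread, N and night draw times. They are not estimates of this trial's error rate.

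The practical risk lies mainly with weak rhythms or large person-to-person differences. It would be tempting to add that clear rhythms are never affected, but that is too strong. With group amplitude 0.7 residual SD, person-to-person SD 0.7, independent errors and N = 20, data are called rhythmic in 99% of trials by pooled rows, 98% by the mean curve and 88% by the participant-level test.

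**What to change.** Make the participant the unit of analysis and say so.

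1. Fit a cosinor to each participant's 10 values, and state whose 24-hour mean is used for normalisation.
2. Replace the R² p-value with Hotelling's T² on the group mean (cos, sin) vector, referred to F with (2, N − 2) df.
3. Base the lean-obese comparison on the same participant-level coefficients. One option is a two-sample Hotelling test, F with (2, N1 + N2 − 3) df, for any difference in rhythm. Add separate delta-method or participant-bootstrap intervals for the amplitude and acrophase differences, because the joint test does not separate them.
4. If a population-mean cosinor was already used, report its participant-level test and df in place of the R² p-value.

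The cost is a change of wording and a few lines of R on existing data, with no new measurements. Power for small rhythms falls against pooled rows: with independent errors, own-mean scaling, N = 20 and amplitude 0.3 residual SD, it is 69% against 79-80%. Part of that gap reflects the inflated level of the pooled test. Against a mean-curve fit, power rises (69% against 56%). Hotelling's T² is one valid participant-level test among several; what matters is that the variability between people enters the test.

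### With one 24-hour cycle and no trend term in the cosinor, a steady drift over the inpatient stay can be declared a 24-hour rhythm with a plausible peak time

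*Combined protocol and SAP*

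**What the plan says.** The Study Protocol section describes one cycle of observation: "The five-day diet was followed by an inpatient visit for a 24-hour assessment of NP levels and BP". Blood is taken through a catheter, "a total of 5 times during wakefulness (7 am to 10 pm), and 5 times during sleep (10 pm to 7 am". Daytime draws are tied to meals at 8 am, 11 am, 2 pm, 5 pm and 8 pm. Night draw times, admission time and the time of the first draw are not given. No second cycle and no repeat draw at the starting clock time is described.

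The Statistical Analyses section fits a mesor, an amplitude and a phase at a fixed 24-hour period, and the software "tests the overall significance of the cosinor model using an F-ratio". The rhythm rule is: "Data was considered rhythmic if the p-value of the R^2 of the cosine function was <0.05". The input is scaled: "The cosinor analysis of the normalized analyte values (normalized to the 24-hour mean value". Rhythm parameters come from a grouped analysis of lean and obese participants. The text does not say whether that means pooled values, averaged individual coefficients or a fit to the mean curve. Amplitude and acrophase are the lean-obese comparisons, and acrophase is the peptide-BP comparison. No trend term, detrending or lack-of-fit check is described.

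For BP only, a lead-in day is provided: the monitor is started a day "prior to the 24-hour inpatient visit to allow the participants to become accustomed to the device".

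**The concern.** The F-ratio asks whether a cosine fits better than a flat line. It does not ask whether the series returns to where it started, which is what separates a rhythm from a one-way change. With one cycle, and if participants start at a common clock time, hours into the stay and clock time are the same variable up to a constant. Dividing by the 24-hour mean removes level but not slope.

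The catheter and the ward setting begin with the visit. Meals change from three plus snacks to five small ones, with distilled water supplied. Any of these could produce a gradual change in natriuretic peptides, renin or aldosterone, although the documents do not show that they do.

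At stake is the trial's main inference. A drift read as rhythm would be reported with an amplitude and a believable peak time. A drift that differed between lean and obese participants would appear as a difference in amplitude or acrophase. Because BP had a lead-in day and blood did not, drift could also move one acrophase in the peptide-BP comparison and not the other.

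**Working it through.** **The plan's own figure.** The documents give no sample size, SD or effect size for the cosinor. The one figure that can be reproduced is the BP reading count: 16 h × 3 per hour = 48, plus 8 h × 2 per hour = 16, total 64. This agrees, and it shows that the BP series analysed is also a single cycle.

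**Inputs from the documents.** Ten draws; model M + AMP·cos + error; F-test on 2 df; threshold 0.05.

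**Assumptions.** Day draws at 8, 11, 14, 17 and 20 h (the listed times could be meal times shortly after the draws); first draw at 8 am; several spacings of five night draws within 10 pm to 7 am, plus an evenly spaced grid; linear drift; 10 to 40 participants per group; residual SD 0.15 to 0.30 of the mean.

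**Step 1: a straight line over a full cycle.** Let y = 1 + d(s/24 − 1/2), with s the hours since the first draw. Its first harmonic is −(d/π)·sin(2πs/24).
- Share of variance explained: [d²/(2π²)] / [d²/12] = 6/π² = 0.608.
- False amplitude for d = 0.20: 0.20/π = 0.064.
- False peak: 18 h after the start for a rise, 6 h after for a fall.

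**Step 2: the ten-draw grids.** R² runs from 0.505 (night draws evenly spaced from 10 pm to 7 am) to 0.691 (every 1.5 h from 11 pm to 5 am). A 20% fall gives an amplitude of about 7%, peaking at about 12:45 to 13:45. A 20% rise gives about 6%, peaking at about 00:45 to 01:45. If sampling started at 10 pm instead, a fall would peak near 3 am. On the 64-reading BP grid, R² is 0.61.

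**Step 3: fit to ten group means, no noise.** With 2 and 7 df, p = (1 − R²)^3.5. R² = 0.505 gives 0.495^3.5 ≈ 0.085; R² = 0.691 gives 0.309^3.5 ≈ 0.016. Passing needs R² above 1 − 0.05^(1/3.5) = 0.575, so some night schedules pass and others fail.

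**Step 4: simulated share of pure-drift data declared rhythmic.** N is per group; drift is over 24 h.

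| Scenario | Pooled values | Individual coefficients | Mean curve |
|---|---|---|---|
| N 20, SD 0.15, drift 20% | 97-99% | 93-96% | 20-52% |
| N 20, SD 0.15, drift 10% | 48-55% | 38-44% | 14-24% |
| N 10, SD 0.30, drift 10% | 11-13% | 7-9% | about 7% |
| No drift | 6-7% | about 5% | about 5% |
| Any of these drifts, linear term added | 6-7% | about 5% | about 5% |

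With a smaller assumed SD of 0.10, a 10% drift and a participant-level test, the share is about 55-94% for 15 to 30 participants. At SD 0.20 it is about 18-39%.

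**Step 5: cost of the linear term.** For the least favourable peak times the variance inflation is 2.0 to 3.2, so the amplitude SE grows by √2.0 = 1.4 to √3.2 = 1.8. For a true 5% rhythm peaking at 2 am (N 20, SD 0.15), power falls from 85% to 53% with pooled values and from about 76-82% to 38-44% with individual coefficients. For an 8 pm peak, pooled power barely changes (88% against 87%).

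**The case against.** A reader might infer that any steady rise or fall will pass as a rhythm. The documents do not support that. Under a mean-curve fit even a noise-free line can miss p < 0.05, and with noisier data or a smaller drift the false-rhythm rate is close to nominal. The type of grouped fit is not stated, and the drift size in these calculations is an assumption.

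A reader might also infer that drift happened, or that the BP lead-in concedes it for blood. Neither follows: the lead-in is about getting used to the monitor. The plan standardises a good deal, with five days of controlled diet, no caffeine or alcohol, supine rest before each draw, controlled light, set meals and recorded water. These steps reduce the scope for drift. None is an inpatient adaptation period for the blood samples, so they do not exclude a trend that starts with the stay.

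It might be added that drift biases a day-night contrast. No such contrast is planned; the regressions compare lean with obese separately for 24-hour, daytime and nighttime means.

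The strongest objection concerns the remedy. A linear term competes with the cosine for the same signal, and real rhythms peaking near 1-2 am or 1-2 pm would often lose significance. That stands, and it is why the refit should not decide whether an analyte is called rhythmic.

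**Conclusion.** The concern holds as a possibility that the stated rule does not exclude. One cycle, no trend term and a p-value as the only criterion mean that drift can be reported as rhythm with a plausible acrophase. For a 20% drift the false amplitude is about 6-7% of the mean. The share of pure-drift data declared rhythmic runs from near nominal to nearly all across the assumed scenarios. These sizes rest on assumed drift, noise, sample size, night draw times and an 8 am first draw, and on which reading of the grouped fit applies. The documents give no evidence that drift occurred, or that it differed between lean and obese participants. What is supported is that a significant plain cosinor alone cannot establish a repeating 24-hour rhythm in these data.

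**What to change.** Keep the plain cosinor as the primary rhythm test and for estimation. For each analyte, add one sensitivity refit with a linear term in hours since the first draw. Report amplitude, acrophase and p-value from both models. Where the cosine terms do not survive, state that rhythm and drift cannot be separated within one cycle; do not conclude that rhythm is absent. Alongside, state the first-draw time, the night draw times and the type of grouped fit, since the size of the problem depends on them.

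The cost is some SAP wording and one more model per analyte on data already collected. The downside is precision: the amplitude SE rises by up to about 1.4-1.8 times, and power can roughly halve for peaks near 1-2 am or 1-2 pm. The refit must therefore inform interpretation and not override the primary rhythm call.

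A closing sample at the starting clock time would not replace the term. In simulation with that sample and a 20% drift (N 20, SD 0.15), the plain cosinor still declared rhythm in 96% of runs with pooled values and 93% with individual coefficients. The documents are also written in the past tense, so changing the sampling is probably no longer possible.

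### Does comparing NP and BP rhythms by acrophase require the plan to name an interval or test for the phase difference?

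*Combined protocol and SAP*

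**What the plan says.** All the relevant text is in the Statistical Analyses section, apart from the sampling scheme.

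- **NP against BP:** "The reported cosinor parameter of interest while comparing the normalized NP and BP rhythms was acrophase".
- **Lean against obese:** "The cosinor parameters of interest while comparing the normalized NP rhythms between lean and obese individuals were the amplitude and acrophase".
- **Unit of analysis:** "The rhythm parameters are based on the grouped analysis of the lean and obese population groups". The section does not say whether a curve is fitted to pooled data or to each participant and then combined.
- **Inference on the cosinor fit:** the package "tests the overall significance of the cosinor model using an F-ratio", and "Data was considered rhythmic if the p-value of the R^2 of the cosine function was <0.05".
- **Other inference:** "Linear regression models were used to assess the relative percentage difference with a 95% confidence interval", applied to 24-hour, daytime and nighttime mean levels. Also "Continuous data were compared using the Wilcoxon rank-sum test", which comes straight after the baseline descriptives.
- **Level:** "A two-sided type-I error of <0.05 was considered statistically significant for all analyses".

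The Study Protocol section gives 10 blood draws per person, five by day and five by night, and places the NP and BP assessment at the same inpatient visit. The 24-Hour Ambulatory BP section gives at most 64 BP readings.

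**The concern.** The NP-BP comparison rests on one quantity, the gap between two peak times, and none of the named methods is assigned to it. The cosinor test asks whether a single series is rhythmic. The regression interval concerns mean levels. The rank-sum test is for independent samples, whereas NP and BP come from the same people. Clock time also wraps round midnight, which ordinary means and ranks ignore.

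If a report showed two significant rhythms and two acrophases about 1 h apart with no measure of precision, a reader could not tell a phase shift from sampling error. Nor could a small gap be read as evidence that the rhythms coincide. Lean against obese raises a similar question for acrophase and amplitude.

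**Working it through.** **1. Is there a design figure to reproduce?** No. The documents give no sample size, power, expected phase gap or standard error for acrophase. The one checkable count is the BP readings: 16 h × 3 per hour + 8 h × 2 per hour = 48 + 16 = 64, as stated.

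**2. Can the named methods be stretched to cover the gap?** Rank-sum cannot do so for NP against BP. If the grouped analysis yields one acrophase per series, a one-against-one rank-sum test gives p = 1.0 whatever the values. With per-participant acrophases it would ignore pairing. Wrap-around matters too: 23 h and 1 h have arithmetic mean 12 h but circular mean midnight. For lean against obese the groups are independent, so the pairing objection falls away and only the circularity remains.

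**3. Does the fit the plan names carry the information needed?** Yes. A least-squares cosinor gives cosine and sine coefficients with a covariance matrix. With roughly even sampling and N pooled readings, the standard error of acrophase in hours is approximately

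SE ≈ (24/2π) × √(2/N) ÷ (amplitude/residual SD).

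Assume 10 participants and an amplitude-to-residual-SD ratio of 0.5 for both series:

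- NP, N = 100: 3.82 × 0.141 ÷ 0.5 = 1.08 h
- BP, N = 640: 3.82 × 0.0559 ÷ 0.5 = 0.43 h
- 95% half-width of the difference: 1.96 × √(1.08² + 0.43²) ≈ 2.3 h

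With 40 participants this halves to about 1.1 h. Exact calculation on assumed draw times gives 2.27–2.32 h and 1.13–1.16 h. Ratios from 0.25 to 1.0 with 10 to 40 participants span about 0.6 to 4.7 h. This formula treats readings as independent and omits person-to-person phase spread, so step 4 adds that.

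**4. How large a gap could chance produce?** Simulation, no true NP-BP difference. All inputs other than the numbers of readings, the BP schedule and the daytime draw times (taken as the meal times) are assumed: night draws at 23:00, 01:00, 03:00, 05:00 and 06:45; phase SD 2.25 h; NP-BP phase correlation 0.35; NP amplitude 0.15 and residual SD 0.20; BP amplitude 0.10 and residual SD 0.10, all relative to the person's own mean.

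| Participants | Gap ≥ 1 h | Gap ≥ 2 h | Paired bootstrap 95% half-width |
|---|---|---|---|
| 10 | 41% | 11% | 2.2 h |
| 20 | 26% | 2% | 1.6 h |
| 40 | 10% | 0.1% | 1.2 h |
| 60 | 4% | 0% | 1.0 h |

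Independent re-runs agreed within about one percentage point.

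**5. How firm are these figures?** Not firm. Varying phase SD (1.5–3 h), correlation (0–0.7) and NP amplitude (0.10–0.20) moves the 1 h figure at 20 participants between 6% and 51%. Changing only the NP residual SD from 0.10 to 0.30 moves it from 15% to 35%. Varying that together with the other three spans about 1% to 60%.

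**6. Lean against obese.** With 20 per group, chance gaps of at least 1 h occur in 39%. At 20 participants the variance of the gap is 0.78 h² for NP-BP, 0.94 if only the correlation is removed, 0.91 if only BP is cut to 10 readings, and 1.28 in the lean-obese setting. The rise of 1.28 − 0.78 = 0.50 therefore owes 0.16 to lost pairing and 0.13 to fewer readings, each taken alone. The remaining 0.21 reflects the assumed noisier NP signal and the joint effect of the changes. A normal approximation ties these to the percentages: 1/√0.78 = 1.13 gives 26%, and 1/√1.28 = 0.88 gives 38%.

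**The case for a change.** The strongest case for a change is that acrophase is the only parameter reported for NP against BP, that a significance level is not a method, and that even a descriptive gap needs a measure of precision. The remedy would also be cheap: an interval from resampling whole participants uses existing data.

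Much of this stands. The text assigns no method to a phase difference, rank-sum does not suit paired series, and a report is better with an interval than without one.

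It does not follow that the plan is wrong. The text never says that two rhythmicity p-values will be read as evidence for or against a phase shift. The 1 h gap that drives the illustration appears nowhere in the documents. Calling acrophase a reported parameter is compatible with description, and the level set for all analyses suggests a test may have been intended. No single interval is plainly best: the percentile bootstrap covered only 90% with 10 participants at mid-range, against 94% with 20 or more. Treating the series as unpaired, the likeliest shortcut, widened the interval by 11–13% at correlation 0.35, which errs towards caution.

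**Conclusion.** The gap in the text is real, but it is one of detail and calls for no change. The plan names the quantity, the model and the significance level, and leaves open how precision is attached to a difference in peak times. A competent analyst can fill that from the fitted coefficients or by resampling participants, with differences taken on the 24-hour circle. No rule the plan states is shown to give a wrong acrophase or a wrong conclusion.

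The illustrated size, a chance gap of at least 1 h in 4% to 41% of trials for 60 down to 10 participants, holds only at one assumed set of inputs. With 20 participants it can lie anywhere from about 1% to 60%. The figures show that interpretation depends on quantities the documents do not give, not that this trial's comparison is unreliable. For lean against obese the case is weaker still, since the groups are independent and the general rank-sum sentence could plausibly apply if acrophases are estimated per participant.

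The judgement would differ for a report that claimed a phase shift, or coincidence, of about 1 h from rhythmicity tests alone. That would be a fault of the report, and nothing in the plan commits the authors to it.
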